#### Management of immune-mediated liver injury caused by immune checkpoint inhibitors (ILICI)

Recommended management of treatment-emergent abnormal hepatic biochemical tests in clinical trials with sabestomig (patients with normal baseline ALT, ASTa)

Treatment Emergent ALT/AST	TBL b Values at Time of Treatment Emergent ALT Elevation	Investigational drugs treatment adjustment and additional therapy	Monitoring and evaluation
Normal	Isolated total blood bilirubin elevation > 3 × ULN	Discontinue investigational drug.	Repeat blood tests d within 2 to 3 days. Initiate close monitoring and evaluation e .
$\leq$ 3 x ULN	Normal. Patients with Gilbert's syndrome: No change in baseline TBL.	Continue treatment.	Repeat blood tests c within 1 to 2 weeks.
> 3 x ULN	Normal. Patients with Gilbert's syndrome: No change in baseline TBL.	Withhold investigational drug. If rising ALT/AST when re-checked, start prednisone/prednisolone 1 mg/kg/d f . If ALT/AST improve to $\leq 3.0$ x ULN, resume treatment after completion of steroid taper to equivalent of prednisone $\leq 10$ mg/day.	Repeat blood tests d within 2 to5 days. Initiate close monitoring and evaluation e .
	TBL $\geq 2 \times ULN$ . Patients with Gilbert's syndrome: Doubling of direct bilirubin.	Discontinue investigational drug. Start prednisone/prednisolone 1 to 2 mg/kg/d f .	Repeat blood tests d within 2 to 3 days. Initiate close monitoring and evaluation e .
> 5 x ULN	Normal. Patients with Gilbert's syndrome: No change in baseline TBL.	Withhold investigational drug. Start prednisone/prednisolone 1 to 2 mg/kg/d f . Resume treatment if elevations downgrade to AST and ALT $\leq 3.0$ x ULN within 14 days, and after completion of steroid taper to equivalent of prednisone $\leq 10$ mg/day. Otherwise discontinue investigational drug permanently.	Repeat blood tests d within 2 to 3 days. Initiate close monitoring and evaluation e . Treatment shall only resume following consultation with a hepatologist and based on a benefit/risk assessment for the affected participant.
> 10 x ULN	Normal or elevated.	Discontinue investigational drug. Start prednisone/prednisolone 1 to 2 mg/kg/d g .	Repeat blood tests d within 2 to 3 days. Initiate close monitoring and evaluation e .

Recommended management of treatment-emergent abnormal hepatic biochemical tests in clinical trials with sabestomig (patients with abnormal baseline ALT, ASTa)

Treatment Emergent ALT/AST	TBL b Values at Time of Treatment Emergent ALT Elevation	Investigational drugs treatment adjustment and additional therapy	Monitoring and evaluation
Elevations			
> bsl	Normal. Patients with Gilbert's syndrome: No change in baseline TBL.	Continue treatment.	Repeat blood tests e within 1 to 2 weeks.
> 2 x bsl	Normal. Patients with Gilbert's syndrome: No change in baseline TBL.	Withhold investigational drug. If rising ALT/AST when re-checked, start prednisone/prednisolone 1 mg/kg/d f . If ALT/AST improve to $\leq 2 \text{ x}$ bsl, resume treatment after completion of steroid taper to equivalent of prednisone $\leq 10 \text{ mg/day}.$	Repeat blood tests d within 2 to 5 days. Initiate close monitoring and evaluation e .
	TBL ≥2 x ULN. Patients with Gilbert's syndrome: Doubling of direct bilirubin	Discontinue investigational drug. Start prednisone/prednisolone 1 to 2 mg/kg/d f .	Repeat blood tests d within 2 to 3 days. Initiate close monitoring and evaluation e .
> 3 x bsl	Normal. Patients with Gilbert's syndrome: No change in baseline TBL.	Withhold investigational drug. Start prednisone/prednisolone 1 to 2 mg/kg/d f . Resume treatment if elevations downgrade to AST and ALT $\leq$ 2 x bsl within 14 days, and after completion of steroid taper to equivalent of prednisone $\leq$ 10 mg/day. Otherwise discontinue investigational drug permanently.	Repeat blood tests d within 2 to 3 days. Initiate close monitoring and evaluation e .
> 5  x bsl	Normal or elevated.	Discontinue investigational drug. Start prednisone/prednisolone 1 to 2 mg/kg/d g .	Repeat blood tests d within 2 to 3 days. Initiate close monitoring and evaluation e .

- a. Use of serum ALT is preferred over AST due to its higher hepatic specificity. ALP is not included in this table as isolated ALP elevation is often related to the underlying malignancy and uncommonly related to ILICI. Furthermore, there are limited published data regarding management of ILICI in patients who develop isolated ALP elevation during ICI treatment.
- b. Measurement of total and conjugated (or direct) bilirubin is recommended to help identify patients with indirect hyperbilirubinemia due to Gilbert's syndrome or hemolysis versus liver injury.
- c. Recommended blood tests include ALT, AST, ALP, GGT, TBL.
- d. Recommended blood tests include: ALT, AST, ALP, GGT, TBL, DBL, CK, INR.
- e. Initial monitoring should be 2–3 times a week. Frequency of monitoring may be adjusted based on clinical scenario and severity of injury. Monitoring should continue until ALT/AST levels return to  $\leq$  3 x ULN, regardless of whether or not the investigational drugs have been discontinued. For recommendations on diagnostic follow-up and evaluation of potential alternative etiologies see Table 1 below.
- f. Oral prednisone/prednisolone: if hepatic biochemical tests worsen on oral prednisone/prednisolone, change to IV (methyl)prednisolone. Once ALT/AST return to ≤ 3 x ULN, corticosteroids can be weaned over 2–4 weeks. Treatment with investigational drug(s) may be resumed with close monitoring, once prednisolone dose ≤ 10 mg/day.
- g. IV (methyl)prednisolone: if worsening continues on IV (methyl)prednisolone, consider adding MMF 500–1000 mg twice daily. Once hepatic biochemical tests return to Grade 1, corticosteroids can be weaned over 4 weeks. Treatment with investigational drug(s) may be resumed with close monitoring, once prednisolone dose ≤ 10 mg/day.
- Abbreviations: bsl: baseline; CK creatinine kinase; DBL direct Bilirubin; GGT Gamma-glutamyl transferase; INR international normalized ratio; IV: intravenous; PO: per os (taken orally); ULN upper limit of normal

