## 6.6.3 Definition of Dose-limiting Toxicity

The DLTs will be evaluated during Part A Dose Escalation. The DLT evaluation period will be 28 days from the first dose of sabestomig on Cycle 1 Day 1. Participants who do not remain in the study for the entire duration of the DLT evaluation period, for reasons other than DLT, will be considered non-evaluable for DLT evaluation and will be replaced with another participant at the same dose level if needed to ensure a minimum of CCI evaluable participants in the ATD and mTPI-2 cohorts, respectively.

A DLT will be defined during Part A Dose Escalation as any  $\geq$  Grade 3 AE as per NCI CTCAE version 5 unless unequivocally due to underlying malignancy or an extraneous cause. The modifications and exceptions to this are detailed below.

The following conditions will be considered as DLTs:

- Any death not clearly due to the underlying disease or extraneous causes.
- Grade 4 imAE.
- Any  $\geq$  Grade 3 non-infectious pneumonitis irrespective of duration.
- Any  $\geq$  Grade 3 non-infectious colitis irrespective of duration.
- Liver transaminase elevation:
  - Isolated liver transaminase elevation > 5 x but  $\le 10$  x ULN that does not downgrade to AST/ALT  $\le 3$  x ULN or less within 7 days after onset with optimal medical management including systemic corticosteroids.
  - Transaminase elevation > 10 x ULN regardless of duration or reversibility.
  - Isolated TBL elevation > 3 x ULN that does not downgrade to ≤ 1.5 x ULN within 7 days after onset with optimal medical management (for participants with Gilbert's syndrome: TBL > 3 x ULN and doubling of direct bilirubin that does not downgrade to baseline value within 7 days).
  - Any increase in AST/ALT > 3 x ULN and concurrent increase in TBL  $\ge$  2 x ULN, regardless or duration or reversibility, where no other reason, other than the investigational product(s), can be found to explain the combination of increases (for participants with Gilbert's syndrome: TBL > 3 x ULN and doubling of direct bilirubin that does not downgrade to baseline value within 7 days).
- Any Grade 3 imAE, including rash, pruritus, or diarrhea (NOTE: this excludes colitis or pneumonitis, as these AEs are already defined above), that does not downgrade to Grade 2 or less within 7 days after onset of the event despite maximal supportive care including systemic corticosteroids.

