#### **Dosing Modification and Toxicity Management Guidelines (TMGs) for Sabestomig**

#### General Considerations Regarding Immune-Mediated Reactions

#### These guidelines are provided as a recommendation to support Investigators in the management of potential imAEs.

Immune-mediated events can occur in nearly any organ or tissue, therefore, these guidelines may not include all the possible immune-mediated reactions. Investigators are advised to take into consideration the appropriate practice guidelines and other society guidelines (eg, NCCN, ESMO) in the management of these events. Refer to the section of the table titled "Other -Immune-Mediated Reactions" for general guidance on imAEs not noted in the "Specific Immune-Mediated Reactions" section. Early identification and management of imAEs are essential to ensure safe use of the study intervention. Monitor patients closely for symptoms and signs that may be clinical manifestations of underlying imAEs. Patients with suspected imAEs should be thoroughly evaluated to rule out any alternative etiologies (eg, disease progression, concomitant medications, infections). In the absence of a clear alternative etiology, all such events should be managed as if they were immune-mediated. Institute medical management promptly, including specialty consultation as appropriate. In general, withhold investigational drug(s) for severe (Grade 3) imAEs. Permanently discontinue investigational drug(s) for life-threatening (Grade 4) imAEs, recurrent severe (Grade 3) imAEs that require systemic immunosuppressive treatment, or an inability to reduce corticosteroid dose to 10 mg or less of prednisone or equivalent per day within 12 weeks of initiating corticosteroids.

Based on the severity of the imAE, treatment with sabestomig should be withheld and corticosteroids administered. Upon improvement to Grade  $\leq 1$ , corticosteroid should be tapered over  $\geq 28$  days. More potent immunosuppressive agents such as TNF inhibitors (eg, infliximab) should be considered for events not responding to systemic steroids. Alternative immunosuppressive agents not listed in this guideline may be considered at the discretion of the Investigator based on clinical practice and relevant guidelines. With long-term steroid and other immunosuppressive use, consider need for *Pneumocystis jirovecii* pneumonia (PJP, formerly known as *Pneumocystis carinii* pneumonia) prophylaxis, gastrointestinal protection, and glucose monitoring.

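### The isolated-bilirubin row in the Appendix I liver table recommends discontinuation above 3 × ULN without the Gilbert's qualifier that every other bilirubin-dependent row carries

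*Protocol*

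**What the plan says.** Appendix I gives two tables for managing liver test abnormalities, one for normal and one for abnormal baseline ALT/AST. In the first table, the row for normal ALT/AST with "Isolated total blood bilirubin elevation > 3 × ULN" recommends discontinuing the drug, repeating blood tests within 2 to 3 days, and close monitoring and evaluation.

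The neighbouring rows treat Gilbert's syndrome separately. Where the drug may continue or is only withheld, the bilirubin condition reads "Normal. Patients with Gilbert's syndrome: No change in baseline TBL". Where raised bilirubin leads to discontinuation, it includes "Patients with Gilbert's syndrome: Doubling of direct bilirubin". The abnormal-baseline table follows the same pattern, for example "TBL ≥2 x ULN. Patients with Gilbert's syndrome: Doubling of direct bilirubin".

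Two other sections bear on this:

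- Section 5.1, Table 9 admits Gilbert's participants with total bilirubin (TBL) up to 3 × ULN, provided direct bilirubin is below 30% of the total and there is no hemolysis. Others are limited to 1.5 × ULN.
- Section 6.6.3, on isolated bilirubin elevation as a dose-limiting toxicity, sets for Gilbert's participants "TBL > 3 x ULN and doubling of direct bilirubin that does not downgrade to baseline value within 7 days".

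**The concern.** Isolated bilirubin elevation with normal transaminases is the pattern in which Gilbert's syndrome most needs to be told apart from liver injury, yet this is the one bilirubin-dependent row that does not do so. Followed literally, it takes a Gilbert's participant off study drug for a fluctuation in indirect bilirubin that Section 6.6.3 would not count at the same TBL threshold.

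What is at stake is a participant's treatment. Such a stop would also be reportable as an adverse event (Section 8.3.5) and would enter the primary safety endpoint of adverse events leading to discontinuation (Section 3, Table 5).

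**Working it through.** **Row count (Appendix I liver tables).**

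- Normal-baseline table, 6 rows: normal ALT/AST; ≤ 3 × ULN; > 3 × ULN with normal TBL; > 3 × ULN with TBL ≥ 2 × ULN; > 5 × ULN; > 10 × ULN.
- Abnormal-baseline table, 5 rows: > baseline; > 2 × baseline with normal TBL; > 2 × baseline with TBL ≥ 2 × ULN; > 3 × baseline; > 5 × baseline.
- The top row of each table (> 10 × ULN; > 5 × baseline) applies at any bilirubin. Bilirubin-dependent rows: 11 − 2 = 9.
- Rows with Gilbert's wording: 4 + 4 = 8. The remaining one is the isolated-bilirubin row.

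**How small a rise meets the row.** Inputs are the trigger of 3 × ULN (Appendix I) and the entry ceiling of 3 × ULN for Gilbert's (Table 9). Entry TBL, *e*, is assumed, since the documents give no distribution. With direct bilirubin unchanged, the rise that reaches the threshold is 3/*e* − 1:

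| Entry TBL (× ULN) | Calculation | Rise to 3 × ULN |
|---|---|---|
| 1.5 | 3/1.5 − 1 | 100% |
| 2.0 | 3/2.0 − 1 | 50% |
| 2.5 | 3/2.5 − 1 | 20% |
| 2.8 | 3/2.8 − 1 | 7.1% |
| 3.0 | 3/3.0 − 1 | any rise |

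Anything beyond these values meets the Appendix I row. None meets the Gilbert's condition in Section 6.6.3, because direct bilirubin has not doubled.

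**Secondary check: abnormal-baseline table.** Raised TBL appears only in the > 2 × baseline row with TBL ≥ 2 × ULN and in the > 5 × baseline row; the > baseline row is limited to normal TBL (unchanged TBL in Gilbert's). Let *b* be baseline ALT/AST in × ULN. With TBL ≥ 2 × ULN, values above baseline and above 3 × ULN but no more than 2*b* match no row. The band runs from above max(3, *b*) up to 2*b*, and exists only when 2*b* > 3, that is *b* > 1.5:

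- *b* = 2: above 3, up to 4
- *b* = 2.5 (general entry ceiling): above 3, up to 5
- *b* = 4: above 4, up to 8
- *b* = 5 (ceiling with liver involvement): above 5, up to 10

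**The case against.** The strongest reply is that the site is already led away from an inappropriate stop.

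- Footnote b, attached to the bilirubin column, recommends measuring direct bilirubin "to help identify patients with indirect hyperbilirubinemia due to Gilbert's syndrome or hemolysis versus liver injury". The tests this row orders include direct bilirubin (footnote d), and its evaluation step points to a work-up of other causes (footnote e).
- Appendix I states its own status: "These guidelines are provided as a recommendation to support Investigators in the management of potential imAEs". It also says "In the absence of a clear alternative etiology, all such events should be managed as if they were immune-mediated", which leaves room where Gilbert's is the clear explanation.
- The table for non-immune-mediated reactions requires no dose change for unrelated events or for laboratory changes judged not clinically significant.
- The trigger equals the Gilbert's entry ceiling, so no eligible participant meets it at an entry value. The other rows, keyed to normal TBL or 2 × ULN, would misclassify such participants from the start and need the qualifier more.

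All of this stands as mitigation. None of it changes the action the row states, and the row does not say what to do when direct bilirubin has not doubled. The point about the trigger holds at entry, but the margin can be a few percent.

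Three stronger readings are tempting and are not supported:

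- *The row contradicts Table 9.* It does not. Under Section 6.1.2, Table 9 governs whether the next dose may be given; above 3 × ULN it holds that dose.
- *Appendix I must match Section 6.6.3.* Section 6.6.3 defines dose-limiting toxicity, and Appendix I is stricter elsewhere: it stops for any Grade 3 cytokine release syndrome, which Section 6.6.3 counts only if it fails to improve within 72 hours. Section 6.6.3 matters here because it shows the criterion the protocol itself uses for Gilbert's.
- *Gilbert's participants would be permanently withdrawn.* The row does not label the discontinuation permanent, though other rows use that word. The resumption wording in footnotes f and g is not attached to this row either, so it is silent on resumption.

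**Conclusion.** The omission is real and worth correcting. One of nine bilirubin-dependent rows lacks the Gilbert's qualifier, and its stated action is wrong for a purely indirect rise in a participant the protocol admits. The size depends on assumed entry bilirubin: the threshold is reached by a 20% rise from 2.5 × ULN and about 7% from 2.8 × ULN. The documents do not give the share of participants with Gilbert's syndrome, so the number affected cannot be estimated. The footnotes and general guidance lower the chance of an inappropriate stop without removing the instruction that would cause it.

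The gap in the abnormal-baseline table is a secondary clarification. A reader might infer that a potential Hy's Law case in that band could go on being dosed or unreviewed; the documents do not support that. Section 6.6.8 interrupts dosing for clinically significant toxicity. TBL of 2 × ULN or more exceeds the Table 9 limit for anyone without Gilbert's, so Section 6.1.2 blocks the next dose. Appendix G 4.2 and G 5 require reporting as a serious adverse event and a causality review, and the Appendix I table for other immune-mediated reactions gives fallback holds. What is missing is a single row stating the action.

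**What to change.** In the isolated-bilirubin row, add: *in participants with Gilbert's syndrome, discontinue only if TBL exceeds 3 × ULN and direct bilirubin has doubled; otherwise withhold until the Table 9 limits are met.* This applies the protocol's own criterion. The trade-off is that a Gilbert's participant with an early, purely indirect signal is held and retested rather than stopped at once.

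Optionally, add a row to the abnormal-baseline table for ALT/AST above baseline and above 3 × ULN but no more than 2 × baseline, with TBL ≥ 2 × ULN (for Gilbert's, doubled direct bilirubin). The action would be to withhold, repeat tests within 2 to 3 days, evaluate under Appendix G, and discontinue with steroids if no cause other than the study drug is found. The cap at 2 × baseline is needed so that the row does not overlap the existing discontinue-plus-steroids row. Immediate discontinuation should not be copied from the normal-baseline table: at a baseline of 5 × ULN, an ALT of 5.1 × ULN would trigger it, a rise of 5.1/5 − 1 = 2%.

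The cost is one reworded row and, if wanted, one new row in an annex that is versioned separately from the protocol. Sample size and planned analyses are unaffected.

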#### **Dosing Criteria for Cycles** $\geq 2$

Following completion of the first treatment cycle, participants may receive additional treatment with sabestomig when the following conditions are met:

- The participant does not meet any criteria for discontinuation of IMP as listed in Section 7.1
- The participant has adequate marrow, renal, and liver function, outlined in Table 9. Note: Laboratory evaluations must be performed up to 3 days prior to initiation of each cycle of treatment; transfusion and granulocyte colony stimulating factor support is permissible.
- If the participant experiences an AE following administration of study intervention in the previous dosing cycle, the participant must not meet criteria for dose omission or permanent discontinuation and must meet retreatment guidelines as outlined in the toxicity management guidelines as defined in Appendix I.

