## 7. DISCONTINUATION OF STUDY INTERVENTION AND PARTICIPANT DISCONTINUATION/WITHDRAWAL

## 7.1 Discontinuation of Study Intervention

It may be necessary for a participant to permanently discontinue (definitive discontinuation) study drug. Note that discontinuation from study drug is NOT the same thing as discontinuation from the study.

Participants may be discontinued from study drug in the following situations:

- Confirmed disease progression by PET-CT.
- An AE that meets criteria for discontinuation of study drug (as defined in Sections 6.6.3 and 6.6.8 and the Toxicity Management Guidelines, Appendix I) or in the opinion of the Investigator or AstraZeneca warrants discontinuation of further dosing.
- Investigator determination that the participant is no longer benefiting from study intervention.
- Participant decision. The participant is at any time free to discontinue treatment, without prejudice to further treatment.
- Pregnancy or intent to become pregnant (Section 8.3.10).
- Non-compliance with the CSP (Investigator or participant).
- Participant incorrectly initiated on study intervention.
  - When the reason does not impact safety consider the risk/benefit to the participant of stopping treatment.
- Unexpected, significant, or unacceptable risk to the participants enrolled in the study.
- AstraZeneca termination of study for reasons including but not limited to unfavorable risk/benefit or change in drug development plan.

If study drug is permanently discontinued, the participant will remain on study to be evaluated for protocol-specified assessments including follow-up of any AEs and survival follow-up. At the time of study drug discontinuation, the participant will be followed-up for safety and a visit will be performed 30 and 90 days after receiving the last dose of sabestomig.

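### Four liver-toxicity rows order sabestomig discontinued with no resume rule, yet carry a footnote saying treatment may be resumed

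*Protocol*

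**What the plan says.** Protocol Appendix I, in the part on immune-mediated liver injury, has one table for participants with normal baseline ALT/AST and one for abnormal baseline. Rows that call for a temporary stop say *Withhold* and state when dosing may restart. Rows that say *Discontinue* state no restart rule. Four of them read "Discontinue investigational drug. Start prednisone/prednisolone 1 to 2 mg/kg/d" followed by a footnote mark, f or g.

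Footnote g, on intravenous steroids, ends: "Once hepatic biochemical tests return to Grade 1, corticosteroids can be weaned over 4 weeks. Treatment with investigational drug(s) may be resumed with close monitoring", provided prednisolone is at or below 10 mg/day. Footnote f, on oral steroids, says that after ALT/AST fall to ≤ 3 x ULN "corticosteroids can be weaned over 2–4 weeks. Treatment with investigational drug(s) may be resumed with close monitoring", with the same prednisolone condition.

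The > 5 x ULN row, a milder rise, is a *Withhold* row. It requires a fall to ≤ 3.0 x ULN within 14 days and a steroid taper, then says "Otherwise discontinue investigational drug permanently". It adds: "Treatment shall only resume following consultation with a hepatologist and based on a benefit/risk assessment for the affected participant".

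On later doses, Section 6.1.2 (dosing criteria for cycles ≥ 2) requires that "The participant does not meet any criteria for discontinuation of IMP as listed in Section 7.1". After an adverse event it also says "the participant must not meet criteria for dose omission or permanent discontinuation and must meet retreatment guidelines", pointing to Appendix I. Section 7.1 is about definitive discontinuation. Its list opens "Participants may be discontinued from study drug in the following situations" and includes adverse events that meet the criteria in Sections 6.6.3 and 6.6.8 and Appendix I.

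**The concern.** A site managing a severe liver event finds two instructions in the same table cell: the row says stop, and its footnote says treatment may restart. Footnote g is the clearer case, because no *Withhold* row carries it and its resume sentence therefore has nothing else to refer to. Taken literally, the process for redosing is lighter after a rise above 10 x ULN than after one above 5 x ULN.

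What is at stake is participant safety and uniform conduct: two sites could handle the same event in opposite ways, each citing the annex. Adverse events leading to discontinuation are also a primary safety endpoint (Protocol Section 3), so the same event could be classified differently from site to site.

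**Working it through.** No sample size or error rate is involved. The check sets each row beside its footnote and then asks whether other text decides between them.

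**Step 1. All rows carrying f or g** (Appendix I, both liver tables; bsl = baseline, TBL = total bilirubin)

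| Baseline | Row | Action | Resume rule in the row | Mark |
|---|---|---|---|---|
| Normal | > 3 x ULN, TBL normal | Withhold | ≤ 3.0 x ULN; prednisone ≤ 10 mg/day | f |
| Normal | > 3 x ULN, TBL ≥ 2 x ULN | Discontinue | none | f |
| Normal | > 5 x ULN, TBL normal | Withhold | ≤ 3.0 x ULN within 14 days; ≤ 10 mg/day; otherwise permanent stop; hepatologist and benefit/risk step | f |
| Normal | > 10 x ULN | Discontinue | none | g |
| Abnormal | > 2 x bsl, TBL normal | Withhold | ≤ 2 x bsl; ≤ 10 mg/day | f |
| Abnormal | > 2 x bsl, TBL ≥ 2 x ULN | Discontinue | none | f |
| Abnormal | > 3 x bsl, TBL normal | Withhold | ≤ 2 x bsl within 14 days; ≤ 10 mg/day; otherwise permanent stop | f |
| Abnormal | > 5 x bsl | Discontinue | none | g |

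Footnote f marks 6 rows (4 Withhold, 2 Discontinue) and g marks 2 (both Discontinue). Rows where the footnote contradicts the action: 2 + 2 = 4 of 8. A fifth Discontinue row, isolated bilirubin > 3 x ULN, carries neither footnote.

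**Step 2. Conditions for restarting, side by side.** Footnote g asks for Grade 1 liver tests, a steroid wean, prednisolone ≤ 10 mg/day and close monitoring. It lacks the 14-day limit and permanent-stop default of the > 5 x ULN and > 3 x bsl rows, and the hepatologist and benefit/risk step of the > 5 x ULN row.

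**Step 3. Which instruction governs.** The first test in Section 6.1.2 is whether a Section 7.1 criterion is met. Section 7.1 takes in Section 6.6.3 and Appendix I. Section 6.6.3 lists transaminases > 10 x ULN, and ALT/AST > 3 x ULN with TBL ≥ 2 x ULN where only the study drug explains it; in both cases duration and recovery do not matter. This favours the row. However, Section 6.1.2 also makes the Appendix I retreatment guidelines a dosing condition, and those guidelines include f and g.

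**Step 4. How far Section 6.6.3 backs up the abnormal-baseline rows.** Let baseline be b x ULN and assume that abnormal means b > 1.

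- The > 5 x bsl row starts at 5b x ULN. It starts at or above 10 x ULN when 5b ≥ 10, that is b ≥ 2. For b between 1 and 2 it starts between 5 and 10 x ULN; at b = 1.5 it starts at 7.5 x ULN. Between the row's start and 10 x ULN, the Section 6.6.3 entry for isolated elevations applies only if values do not return to ≤ 3 x ULN within 7 days.
- The abnormal-baseline bilirubin row starts at 2b x ULN. The combined entry needs > 3 x ULN, so it reaches the whole row only when 2b ≥ 3, that is b ≥ 1.5, and then only for drug-attributed cases.

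Table 9 admits ALT/AST up to 2.5 x ULN (5 x ULN with liver involvement), so baselines in these ranges are eligible.

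**The case against.** The strongest reply is that the row plainly controls and the footnote sentence is leftover wording. The Section 6.1.2 test depends on whether a criterion is met, so the permissive verb in Section 7.1 does not weaken it. Section 6.6.3 is written for dose-limiting toxicities in Part A, but Section 7.1 adopts its definitions with no such limit.

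Other controls also stand in the way of redosing: the Table 9 liver limits before each cycle, the 12-week limits in Section 6.7 and the Appendix I general considerations, the permanent stop there for Grade 4 and certain recurrent Grade 3 immune-mediated events, and the Appendix G reporting and joint review when bilirubin is also raised.

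Most of this stands, and it makes the row the better reading. It does not remove the contradiction. The guidelines that Section 6.1.2 tells the site to satisfy contain the footnotes. None of the four rows says the stop is permanent, although the > 5 x ULN row uses that word, so a site has a textual reason to treat the stop as reversible. The other controls restrict redosing without saying whether a Discontinue row ever allows it.

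A reader might also infer that footnote f conflicts with three of its four Withhold rows (> 5 x ULN, > 2 x bsl, > 3 x bsl). The documents do not support that. In f, ≤ 3 x ULN is the trigger for weaning steroids. The only condition attached to its resume sentence is prednisolone ≤ 10 mg/day, which every Withhold row also requires. A site can satisfy row and footnote together, so f omits some of those rows' conditions without contradicting them.

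**Conclusion.** The contradiction is real and limited to four of the eight rows marked f or g. On the two g rows the resume sentence has no harmless reading. On the two f rows it could be read as meant for the Withhold rows that share the footnote, but nothing says so.

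A reader might go further and infer that the protocol authorises rechallenge after the most severe liver injury. Sections 6.1.2, 7.1 and 6.6.3 taken together point the other way. That support is least complete for > 5 x bsl with a baseline below 2 x ULN, which Section 6.6.3 does not fully cover.

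This is a documentation defect that bears on safety. The conclusion assumes that *Discontinue* differs from *Withhold*, as the tables' consistent usage suggests, and that an abnormal baseline means above 1 x ULN. The documents give no event frequency, so the number of participants affected cannot be estimated.

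**What to change.** - Delete the resume sentence from footnote g.
- In footnote f, limit the resume sentence to the Withhold rows and add *subject to the row's own resume conditions*.
- Write *Permanently discontinue* in the four rows. If rechallenge is intended for any of them, state it in the row itself, with conditions no looser than those of the > 5 x ULN row.

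The cost is a few words. Appendix I is versioned separately from the protocol, and substantial updates to it go through submission and approval, so the edit can go into its next update. No analysis or sample size changes.
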